#### b. Inclusion and Exclusion Criteria

# CV Wizard – Clinical Decision Support Tool (Study Aim 1)

NOTE: Individual patients are not being enrolled for this clinic-randomized study. The goal of the study is to examine the uptake and impact of implementing CV Wizard into regular care processes. In this clinic-randomized trial, the intervention is provided at the clinic level and targets clinic processes that are part of routine patient care. CV Wizard will automatically identify patients age 40-75 years with either (a) reversible risk of cardiovascular disease (CVD) >10%, (b) diabetes  $+ \ge 1$  uncontrolled risk factor or high A1c, or (c) existing atherosclerotic cardiovascular disease (ASCVD)  $+ \ge 1$  uncontrolled risk

factor for CVD events. However, clinics can *manually* run the CV Wizard tool for any patient aged 18 and older.

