## **Primary Outcome Measures**

- **Study Aim 1:** Compare patients' change in reversible risk in the Arm 1 vs. Arm 2 CHCs (in months 18-35)
- **Study Aim 2**: Assess whether the revised implementation support materials expedite CDS adoption
- **Study Aim 3:** Use mixed methods to identify multi-level barriers / facilitators to adoption of the CDS tool

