### **Intent to Treat Analysis**

Differences in change in outcomes will assessed using multi-level mixed models. Intra-class correlation coefficients will be obtained at the patient, clinic, and CHC organization levels for each outcome showed that much organization-level variance could be attributed to the clinic level. Thus, clustering was accounted for by random effects for clinic and patient, and a fixed effect for organization. Analyses will adjust for fixed effects: distribution of eligible patients by age, race / ethnicity, gender, rural / urban status, and federal poverty level (FPL) at index visit; number of ambulatory visits during the follow-up period; and time from index to last visit. These variables were selected *a priori* and will be confirmed by descriptive analyses, to determine whether there are significant differences between baseline intervention and control organization and patient characteristics. After checking distributions, negative binomial mixed-models or poisson mixed-model will be used for reversible risk analyses, and linear-mixed models for all other outcomes.

Patients diagnosed with diabetes during the follow-up period will be excluded from reversible risk analyses because diabetes might be diagnosed more often with CDSS use. Presence of diabetes raises reversible risk estimations even if CVD risk factor control was addressed; this exclusion will remove the possibility of confounding based on likelihood on new diabetes diagnosis.

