#### **Effect of Treatment on the Treated Analysis**

Per-protocol analyses require adjusting for loss to follow-up and off-protocol therapies or treatments, but if group differences vary too greatly, model misspecification can yield biased estimates. Propensity score methods are an alternative. We will match intervention organization patients in three categories of tool use (never used during follow-up, used once, used more than once) to control organization patients. Counts of tool use will include use at index visit or subsequent study period visits, excluding the last visit. Matching variables will include age, FPL, outcome of interest at baseline, race / ethnicity, sex, count of ambulatory care visits post-index

visit, time from index visit to last study period visit, and clinic rural / urban status. Propensity scores will be estimated using nearest-neighbor matching with replacement.

As analyses in other settings indicated CV Wizard's potential for greater impact among patients with higher baseline risk, analyses of change in reversible risk will be stratified by baseline risk <10% or ≥10%. The assumption being that patients with lower baseline risk are less likely to improve. Additionally, we will run analyses by quartile of baseline reversible risk among patients for whom the tool was ever used during follow-up, matched to controls as described above. Analyses of change in reversible risk will include all patients meeting study inclusion / exclusion criteria; for other outcomes, analyses were restricted to patients with uncontrolled baseline risk. Linear mixed models will be used for all outcomes and checked for normality of residuals.

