#### Statistical Power

To conservatively calculate power for our main outcome (CVD risk score) we estimated 60 clinics with >35 high-CVD risk patients, randomized to two arms; then, using means and standard deviations for this measure from previous studies, we varied effect size associated with the group x time interaction and intraclass correlation. We examined a 1.5%, 2%, 3% greater absolute reduction in risk score over time in intervention vs. control CHCs. Aggressive management can reduce 10-year CVD risk by an absolute 4-5% in high-risk patients in a short time. We do not expect so large an effect and have power to detect smaller effects. **Supplement Addendum (Aim 2b).** This is a 2x2 repeated measures design with two groups of subjects measured at two time points. The primary goal is to compare change across time in group 1 (inperson index encounters) to change across time in group 2 (VC index encounters). A conservative estimate (based on preliminary results from the parent study) of 6000 patients in group 1 and 6000 in group 2 achieve 100% power to detect a difference in mean changes in CVD risk score of 5.0, with a standard deviation of 9.1 at the first time point, a standard deviation of 9.1 at the second time point, and a correlation between measurement pairs of 0.200. The significance level (alpha) is 0.050 using a two-sided, two-sample t-test.

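### The intent-to-treat analysis allows a Poisson mixed model for reversible risk, a percentage with no stated unit, so the standard error of the primary comparison can be arbitrary

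*Combined protocol and SAP*

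**What the plan says.** The Primary Outcome Measures list (section 6.a) defines the Aim 1 outcome as patients' "change in reversible risk in the Arm 1 vs. Arm 2 CHCs". The outcome is on a percentage scale. One route by which the tool flags a patient (section 5.b) is "reversible risk of cardiovascular disease (CVD) >10" percent, and in the Effect of Treatment on the Treated section "analyses of change in reversible risk will be stratified by baseline risk <10% or ≥10" percent. Risk is calculated at the index visit and at every follow-up encounter (section 7.a, Quantitative Data).

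For the intent-to-treat comparison the plan says that, once distributions have been checked, "negative binomial mixed-models or poisson mixed-model will be used for reversible risk analyses". Clustering is handled by "random effects for clinic and patient, and a fixed effect for organization". The section does not say how to choose between the two models, in what unit or rounding reversible risk enters, or whether a scale parameter or robust standard error will be used.

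For the treated-patient analyses, which include the same outcome, the plan says: "Linear mixed models will be used for all outcomes and checked for normality of residuals". The Statistical Power section expresses the effect of interest as an absolute difference of 1.5, 2 or 3 percentage points in change over time.

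**The concern.** A Poisson model is meant for counts, where the unit is fixed and variance equal to the mean is an assumption that can be checked. A percentage has no natural unit of that kind. Multiply it by a constant k and its mean rises by k while its variance rises by k squared. The ratio of the true to the Poisson standard error therefore changes by the square root of k, with no new information.

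The random effects do not repair this. They absorb stable differences between patients and between clinics. A comparison of change is driven by variation between visits within a patient, and the Poisson model sets that equal to the mean.

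The validity of the primary test is at stake. Under some permitted choices it would reject far too often when the tool has no effect; under others it would lose most of its power. The choice is left until the distributions have been examined.

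**Working it through.** **Inputs.** The only variability figures are in the Supplement Addendum (Aim 2b) power statement: SD 9.1 at the first time point, then "a standard deviation of 9.1 at the second time point, and a correlation between measurement pairs of 0.200". They are given for a CVD risk score and described as based on preliminary parent-study results. No mean of reversible risk appears anywhere, so the mean is varied from 5 to 30.

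**The plan's own figure.** SD of change = 9.1 × √(2 × (1 − 0.2)) = 11.51. With 6000 per group, SE = 11.51 × √(2/6000) = 0.210, and 5.0/0.210 = 23.8. Power is 1.000, which agrees with the stated 100%. The parent trial gives no numerical power.

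**Standard error ratio.** Take two visits, n patients per arm and mean μ. The variance of the change in log mean per arm is approximately:

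- true: 2 × 9.1² × (1 − 0.2) / (nμ²) = 2 × 66.25 / (nμ²)
- Poisson: 2μ / (nμ²)

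So R = true SE / Poisson SE = √(66.25/μ), whatever the sample size. A nominal 5% test then rejects with probability 2 × (1 − Φ(1.96/R)).

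| Assumed mean (%) | R | Type I error |
|---|---|---|
| 5 | 3.64 | 59% |
| 7 | 3.08 | 52% |
| 10 | 2.57 | 45% |
| 15 | 2.10 | 35% |
| 20 | 1.82 | 28% |
| 30 | 1.49 | 19% |

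R = 3 at μ = 66.25/9 = 7.4 (type I error 51%), and R = 2 at μ = 66.25/4 = 16.6 (33%).

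**Sensitivity to the correlation.** Replacing 0.2 by other values of ρ, R = √(9.1² × (1 − ρ)/μ):

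| ρ | μ = 7 | μ = 10 | μ = 15 | μ = 20 |
|---|---|---|---|---|
| 0.2 | 3.08 | 2.57 | 2.10 | 1.82 |
| 0.5 | 2.43 | 2.03 | 1.66 | 1.44 |
| 0.8 | 1.54 | 1.29 | 1.05 | 0.91 |
| 0.9 | 1.09 | 0.91 | 0.74 | 0.64 |

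**Sensitivity to the unit.** As a 0-1 proportion with mean 0.10, the within-patient variance is 66.25/10000 = 0.0066, and R = √(0.0066/0.10) = 0.26. The Poisson SE is then 1/0.26, or about 4 times, too large. Moving from percent to proportion changes R by √100 = 10.

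**Simulation check.** Skewed (gamma) scores with SD 9.1 were generated for 420 patients with two visits, no true effect and no clinic variance, in 120 runs per setting. Random-intercept models were fitted by maximum likelihood.

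| Model, unit | Mean (%) | ρ | R | Rejections |
|---|---|---|---|---|
| Poisson, percent | 7.5 | 0.2 | 2.89 | 47% |
| Poisson, percent | 10 | 0.2 | 2.34 | 42% |
| Poisson, percent | 15 | 0.2 | 2.04 | 37% |
| Poisson, percent | 20 | 0.2 | 1.77 | 26% |
| Poisson, percent | 10 | 0.8 | 1.22 | 12% |
| Poisson, 0-1 | 10 (0.10) | 0.2 | 0.23 | 0% |
| Negative binomial, percent | 10 | 0.2 | 0.90 | 5% |
| Negative binomial, percent | 15 | 0.2 | 0.95 | 3% |

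With 120 runs, a 42% rate has a standard error of √(0.42 × 0.58/120) = 4.5 points. In a separate simulation with 1050 patients per arm, a linear comparison of mean change rejected in 4.5 to 5.4% of runs.

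The unit matters for the negative binomial model too, because its variance cannot fall below the mean. On a 0-1 scale that floor is 0.10, against a true within-patient variance of 0.0066.

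**The case against.** The strongest reply is that the plan's own check would prevent the harm. The negative binomial model is named first, the choice follows a look at distributions, and section 9 also promises to examine variables before analyses are finalised. With SD 9.1 the marginal variance is 82.8, which is 5.5 to 10 times a mean of 15 to 8, so overdispersion would be plain to see. This largely stands as a statement about what a careful analyst would do. It does not close the gap. Nothing requires the negative binomial model, and an analyst could believe that the patient random effect already deals with overdispersion.

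Several stronger readings are tempting but not supported:

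- A reader might infer that the plan's own figures imply a standard error 2 to 3 times too small. They do not. The SD and correlation belong to the supplement's comparison of in-person with virtual encounters, and the mean has to be assumed.
- A reader might infer that the error is always anti-conservative. On a 0-1 scale, or at high correlation with a high mean, it reverses.
- A reader might infer that count models fail because change can be negative. The plan calculates risk at each visit and uses patient random effects, so change can be modelled from repeated non-negative levels.
- A reader might infer that a linear model is right and the negative binomial wrong, or that using different models for the intent-to-treat and treated-patient analyses is itself an error. Neither follows. The negative binomial model was near nominal in percentage points.

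The calculation is also simplified: two visits, no clinic variance and no covariates. It concerns difference in change. The Quantitative Data section also words the hypothesis as lower scores at follow-up visits, and for that contrast the factor would be smaller.

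**Conclusion.** The concern holds in a limited form. The plan permits, for its primary outcome, a model whose standard error depends on a unit it does not state, and it gives no rule that would exclude that model. In percentage points, with SD 9.1, correlation 0.2 and a mean of about 7 to 17%, the Poisson standard error for difference in change is about 2 to 3 times too small and type I error is roughly 33 to 51%. Over means of 5 to 30% the factor runs from 3.6 to 1.5. At correlation 0.8 it is about 1.3 at mean 10 and below 1 at mean 20 or more.

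A mean near 10 is plausible given the plan's 10% cut-points, but it is an assumption. These are consequences of choosing Poisson, not a prediction that it will be chosen.

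**What to change.** In the Intent to Treat Analysis section:

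1. Delete the Poisson option.
2. State that reversible risk is analysed in percentage points as repeated levels (index and follow-up), with any rounding given.
3. Name one primary model with a free residual variance or dispersion parameter, and add cluster-robust standard errors.

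A linear mixed model would match the treated-patient analyses and the absolute effect in the Statistical Power section. A negative binomial mixed model in percentage points is also acceptable. Whichever is not primary can serve as a sensitivity analysis.

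The cost is SAP wording only. If the linear model is chosen and reversible risk is very skewed, efficiency may be slightly lower.

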#### **Secondary Outcome Measures**

- **Reach: Encounters affected** % clinic encounters where CV Wizard suggests running the full risk assessment tool, i.e., identified a target patient.
- Effectiveness (impact): Patient outcomes 10-year pooled ASCVD risk score change in ASCVD risk score from baseline to last visit of study period (American College of Cardiology-ACC/ American Heart Association - AHA) 10-year pooled ASCVD risk score, 40-75 year olds
- Effectiveness (impact): Patient outcomes last BP ≤140/90 Control of individual CVD risk factors: last BP ≤140/90
- Effectiveness (impact): Patient outcomes last A1c≤8 Control of individual CVD risk factors: last A1c≤8
- Effectiveness (impact): Patient outcomes last LDL<100 Control of individual CVD risk factors: last LDL<100
- Effectiveness (impact): Patient outcomes not current smoker Control of individual CVD risk factors: not current smoker
- Effectiveness (impact): Patient outcomes last BMI ≤25 Control of individual CVD risk factors: last BMI≤25
- Adoption: CDS uptake % of encounters where care team member opts to run the CV
   Wizard risk assessment (explored as both view and print rate and just print rate)
- Implementation: User perceptions Perceived ease of use, usefulness, acceptability of CV Wizard; intent to use it.
- Maintenance over time All measures over 2.5 years of follow-up, Arm 1; 1.5 years, Arm 2.

Table 6. Impact and uptake of the CV Wizard system: Quantitative Measures		
Outcomes, per RE-AIM	Measurement	
Reach:	% clinic encounters where CV Wizard suggests running the full risk assessment tool,	
Encounters affected	i.e., identified a target patient	
Effectiveness (impact):	(i) change in ASCVD risk score (reversible risk; ACC/AHA 10-year pooled ASCVD risk	
Patient outcomes	score, 40-75 year olds; Framingham 30-year CVD risk score, 20-39 year olds).	
	(ii) Control of individual CVD risk factors: last BP ≤140/90; last A1c≤8; last LDL<100;	
	not current smoker; last BMI≤25);	
Adoption: CDS uptake	% of encounters where care team member opts to run the CV Wizard risk	
	assessment	
Implementation: User	Perceived ease of use, usefulness, acceptability of CV Wizard; intent to use it; see	
perceptions	3.3.f.ii	
Maintenance over time	All measures over 2.5 years of follow-up, Arm 1; 1.5 years, Arm 2	
Potential covariates	Measurement	
Patient demographic	Age; gender; race / ethnicity; primary language; poverty level; insurance status at	

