#### **Supplement Addendum**

- (1) Descriptive Analyses (Aim 2a)
  - We will conduct a descriptive analysis on the following process outcomes: (1) Encounter patterns; (2) Rates of missed or cancelled appointments at in-person vs. VC (telephone, video) encounters; (3) Appointment wait times by encounter type, and (4) CV Wizard use (in encounters where there are CV Wizard CDS suggestions by encounter type.
  - We will use standard statistical tests (e.g., chi-square, t-tests) to describe measures in the periods pre- vs. post-COVID's onset.
- (2) Regression Analyses (Aim 2b)
  - Encounter is the unit of analysis.
  - We will assess associations between encounter type and: (1) Action taken on needed care plan components; (2) Up-to-date documentation of BP and A1c by 6 months postindex visit (accounting for whether BP data were taken in person or reported by the patient); and (3) Change in CVD risk factors by end of follow-up period. To do so, we will conduct adjusted regression analyses using longitudinal electronic health record data.

- To assess action taken on needed care, data for each factor will be extracted at each
  visit in the study period. We will use adjusted logistic regression models, with a
  dichotomous outcome of action taken or not taken.
- To assess *impact on individual CVD risk factors*, data for each factor will be extracted at index visit and all visits in the follow-up period (coded as controlled vs. not).
- Generalized linear mixed models (GLMM) with time nested within patients will be used to determine if risk factor control differs across encounter types, to estimate the effect of encounter type on change over time in CVD risk score and BP and A1c control. All encounters for each eligible patient will be included. CVD risk is influenced by factors amenable to clinical intervention (e.g., BP) and others that are irreversible (age); absent intervention, overall risk should increase with age. These analyses will be adjusted for or stratified by potential confounders at the patient, provider, and encounter level. This will include accounting for whether post-index visit encounters were in-person or VC, and the reason for the encounter, as in-person encounters in the post-COVID period may be for different reasons than VC encounters.

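### Five yes/no risk-factor control outcomes are assigned linear mixed models, and the treatment-on-the-treated section adds a residual-normality check that they cannot meet

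*Combined protocol and SAP*

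**What the plan says.** Section 6.a, Secondary Outcome Measures, defines the individual risk-factor outcomes by a threshold or a status, for example "Control of individual CVD risk factors: last BP ≤140/90" and "Control of individual CVD risk factors: not current smoker". A1c, LDL and BMI are handled the same way, which makes five yes/no outcomes. Section 7.a, Quantitative Data, states the matching hypothesis in terms of rates of control. The same list of secondary outcomes also holds one continuous effectiveness measure, the change in 10-year ASCVD risk score.

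Three parts of Section 7.a then choose models:

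- Intent to Treat Analysis: "After checking distributions, negative binomial mixed-models or poisson mixed-model will be used for reversible risk analyses", and "linear-mixed models for all other outcomes". Clustering is handled by "random effects for clinic and patient, and a fixed effect for organization". This section has no residual-normality check.
- Effect of Treatment on the Treated Analysis: "Linear mixed models will be used for all outcomes and checked for normality of residuals". For everything except reversible risk, "for other outcomes, analyses were restricted to patients with uncontrolled baseline risk".
- Supplement Addendum: risk-factor data are coded as controlled or not, and "Generalized linear mixed models (GLMM) with time nested within patients" are used to compare control across encounter types. Logistic regression is named there for whether needed care was acted on.

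**The concern.** A linear mixed model assumes one residual variance and approximately normal residuals. A 0/1 outcome has neither. The ETOT section makes normality a stated check, so for the five indicators the check must fail, and that section says nothing about what follows. The replacement model would then be chosen with the data in view. The variance assumption raises a second question: whether confidence intervals for the risk-factor contrasts are too narrow or too wide. The supplement also uses a generalized model for the same kind of outcome, so the plan is not consistent with itself.

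**Working it through.** The documents give no control rates, intraclass correlation (ICC) or power for the five indicators, so there is no figure of the plan's own to reproduce. All rates, ICCs and unequal splits below are assumptions. The 60 clinics and 35 patients per clinic follow the Statistical Power section.

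1. **Normality check.** At fitted probability p the residual is either 1 − p or −p. Skewness is (1 − 2p)/√(p(1 − p)) and excess kurtosis is (1 − 6p(1 − p))/(p(1 − p)). At p = 0.8 the residuals are +0.2 and −0.8, with skewness −0.6/0.4 = −1.5. At p = 0.9 skewness is −0.8/0.3 = −2.67 and excess kurtosis 5.11. At p = 0.5 skewness is 0 but excess kurtosis is −2.0. No value of p gives normal residuals.

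2. **Constant variance.** The residual variance is p(1 − p): 0.25 at p = 0.5 and 0.09 at p = 0.9, a ratio of 2.8. The assumption is formally wrong. That ratio is not the error in the treatment contrast, which needs its own calculation.

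3. **Standard error of a difference in proportions (independent patients).** With group variances v₁, v₂ and sizes n₁, n₂, the pooled-variance formula gives SE² = v₁/n₂ + v₂/n₁. The true value is v₁/n₁ + v₂/n₂. The ratio of pooled to true SE is the square root of the quotient:

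| Sizes n₁:n₂ | Rates | Calculation | SE ratio |
|---|---|---|---|
| 1:1 | any | numerator equals denominator | 1.00 |
| 1:2 | 0.8 vs 0.9 | √[(0.08 + 0.09)/(0.16 + 0.045)] = √(0.170/0.205) | 0.91 |
| 1:2 | 0.9 vs 0.8 | √(0.205/0.170) | 1.10 |
| 1:4 | 0.10 vs 0.05 | √[(0.0225 + 0.0475)/(0.09 + 0.0119)] = √(0.0700/0.1019) | 0.83 |
| 1:4 | 0.05 vs 0.10 | √(0.1019/0.0700) | 1.21 |

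At a ratio of 0.83 a nominal 95% interval has a critical value of 1.96 × 0.83 = 1.63 true standard errors and misses about 10% of the time.

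4. **Simulation with clustering.** A 0/1 outcome was generated in 60 clinics of 35 patients and analysed with a random-clinic linear model (ICC 0.01 and 0.05, 5,000 runs per setting).
   - 30 vs 30 clinics: model-to-empirical SE ratio 0.987 to 1.017, non-coverage 4.7% to 5.4%.
   - A two-time version with the arm-by-time contrast and equal arms (2,000 runs): ratio 0.97 to 1.005, non-coverage 4.9% to 5.9%.
   - 2:1 split, equal rates (0.6 or 0.9): non-coverage 4.5% to 5.4%.
   - 2:1 split, 0.6 vs 0.7: ratio 0.974 to 1.045.
   - 2:1 split, 0.8 vs 0.9: ratio about 0.90 to 0.91 with non-coverage 7.6% to 8.3% when the larger arm has the higher rate; 1.09 to 1.10 with non-coverage 3.2% when it has the lower rate.

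5. **Which analysis can meet the bad case.** Clinic Identification, Recruitment & Assignment chose the allocation that distributed most evenly over the arms, so the ITT comparison should be near balanced. The ETOT analysis splits intervention patients into three tool-use categories and matches controls with replacement at no stated ratio, so equal groups are not assured. It also keeps only patients uncontrolled at baseline, so each indicator is 0 for everyone at index. If index rows enter the model, their variance is zero while the follow-up variance is p(1 − p).

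**The case against.** The strongest reply is that a linear model for a 0/1 outcome estimates the risk difference, a sensible target here, and that its standard error is nearly right with balanced arms. That stands for the ITT comparison. It does not rescue a normality criterion, and it does not cover unequal groups analysed without robust errors.

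A second reply is that the linear models may be meant for continuous BP, A1c, LDL and BMI. The ITT text speaks of change in outcomes. The ETOT text matches on the baseline value of the outcome, which would be constant for a control indicator among uncontrolled patients. These are hints only: no such continuous outcome is defined for Aim 1, the hypothesis concerns rates of control, and smoking status cannot be read that way.

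A third reply is that Section 9 says distributions will be examined before analyses are finalised. That is a general policy of deciding later; it does not name a model for these outcomes.

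A reader might also infer more than the documents support:

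- That the normality check governs the ITT analysis. It appears only in the ETOT section.
- That every secondary effectiveness outcome is affected. The change in ASCVD score is continuous, and a linear mixed model is conventional for it.
- That the supplement already prescribes mixed logistic models for risk-factor control. It says GLMM and names no link or distribution; logistic regression is named only for action on needed care. The supplement also compares encounter types rather than randomised arms.

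**Conclusion.** The point holds for the five control indicators. The plan defines them as yes/no and models them as Gaussian in both ITT and ETOT, with a check in ETOT that they cannot pass. For a near-balanced ITT comparison the effect on the standard error is within about 3%. With unequal groups and different control rates, the worked cases run from about 10% to 17% too small and about 10% to 21% too large; with equal rates the error largely vanishes. A general claim that the standard errors are invalid is therefore not supported.

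The primary ITT analysis of reversible risk, which uses a count model, and the continuous ASCVD score are untouched. The sizes rest on assumed rates, ICCs and splits. The simulations leave out covariates, the fixed organization effect, variable clinic size and matching with replacement, and they treat the clinic as the randomised unit although the plan assigns by service area. This is a secondary-outcome specification problem that should be corrected because the remedy is cheap.

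**What to change.** For the five indicators, prespecify in both the ITT and ETOT sections a mixed logistic model, and report standardised risk differences with confidence intervals. A linear risk-difference model with cluster-robust standard errors is an acceptable alternative if it is named in advance. Restrict the ETOT normality check to continuous outcomes. Reconcile the ITT and ETOT model statements with the supplement's GLMM for control coded as controlled or not, and state its link. If continuous BP, A1c, LDL or BMI values are what the linear models are for, define them as outcomes and keep them as supportive analyses.

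The cost is a few sentences in Section 7.a and routine code in SAS, which the plan already uses. The downside is slightly slower fitting and a standardisation step.

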#### **Quantitative Data**

To be included in Aim 1 analyses a patient must have at least one visit in the 6 months after the Arm 1 implementation date at an Arm 1 or Arm 2 CHC and at least one additional visit at a study clinic in the 12-month post-index visit period. The first visit is referred to as the index visit. We will describe those who had inadequate follow-up data (did not have at least one additional visit in the post-index period). For each study subject, CVD risk score / risk factor management status will be calculated at index visit and each encounter during follow-up. While the tool can be run for patients of any age, we will restrict our analyses to patients 40-75 years of age.

We will test for between-group differences in baseline characteristics such as age, sex, race and ethnicity, insurance type, visit count, and health status using chi-square, t-test, and nonparametric Wilcoxon rank-sum tests as appropriate. We will also test for association between baseline characteristics and our outcomes of interest. We will examine the number of patients seen in each service area and clinic and each Arm and compare the characteristics of Arm 1 patients for whom the tool was used to those in Arm 1 for whom the tool was not used and to Arm 2 patients. Because the two arms were selected based on clinic size, percent of patients with a diagnosis for hypertension and the percent of patients that use tobacco, we anticipate there will be differences between the two groups resulting in the need to adjust for these differences. We will also examine characteristics at the service area and clinic-level in Arm 1 for whom the tool was used compared to Arm 1 service areas / clinics for whom the tool was not used and Arm 2 service areas / clinics.

Unadjusted trends in the monthly use and view rates for each of the study CHCs will be explored with use rates defined as: the number of encounters where CV Wizard was printed / number of targeted encounters with high-CVD risk patients per month and view rates defined as the number of encounters where CV Wizard was viewed / number of targeted encounters with high-CV risk patients per month.

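### The primary reversible-risk ITT analysis drops patients newly diagnosed with diabetes, an event the tool may cause, and no planned output would show the effect

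*Combined protocol and SAP*

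**What the plan says.** Section 6.a (Primary Outcome Measures) defines the Aim 1 primary outcome as patients' "change in reversible risk in the Arm 1 vs. Arm 2 CHCs (in months 18-35"). Section 7.a (Quantitative Data) describes the ITT comparison as covering every targeted patient at intervention and control clinics.

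Section 7.a (Intent to Treat Analysis) then narrows this: "Patients diagnosed with diabetes during the follow-up period will be excluded from reversible risk analyses", "because diabetes might be diagnosed more often with CDSS use". The plan adds that having diabetes raises the reversible-risk estimate even when risk factors have been addressed, and concludes that "this exclusion will remove the possibility of confounding based on likelihood on new diabetes diagnosis".

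On patients left out of the analysis, section 7.a (Quantitative Data) promises only this: "We will describe those who had inadequate follow-up data". That means patients without a second visit.

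**The concern.** The rule conditions the primary comparison on something that happens after randomisation and that the plan itself says the tool may make more frequent. Such an event is not a confounder of a randomised comparison, so excluding on it does not remove confounding. It does remove the scoring artefact, but it can leave the two arms non-comparable. If Arm 1 diagnoses more patients, Arm 1 loses people whose counterparts remain in Arm 2. If those people's risk follows a different course, the arms differ in mean change even when the tool does nothing.

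The retained set is also no longer ITT as the plan defines it. The exclusion covers reversible-risk analyses only, so blood pressure, A1c, LDL, smoking and BMI are not affected.

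**Working it through.** **Figures in the plan.** For Aim 1 the documents give no SD, ICC, power value or rate of new diabetes, so there is no Aim 1 figure to reproduce. The one complete power statement is the supplement's. SD of change = sqrt(2 × 9.1² × (1 − 0.2)) = 11.51. With 6000 per group and a difference of 5.0, power is 1.000, which agrees with the stated 100%. It has no bearing on this point, except that its SD is borrowed below.

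**Would any planned output show the problem?**
- The description of patients with inadequate follow-up does not cover this exclusion.
- The descriptive statistics under Secondary Analyses cover patients and encounters included in analyses.
- In the Effect of Treatment on the Treated section, "Analyses of change in reversible risk will include all patients meeting study inclusion / exclusion criteria". That does not bring these patients back into the ITT analysis, and matching by tool use would not isolate the effect of the exclusion.
- Whether the exclusion reaches the 10-year ASCVD score is unclear, because Table 6 labels that score as reversible risk. Even if it keeps these patients, it may carry the diabetes label.

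No section counts the exclusions by arm or plans an ITT result without them.

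**Bias from the exclusion, with no true effect.** Change is follow-up minus index, so a negative bias favours the tool. All inputs are assumptions:
- q, the share of targeted patients with undiagnosed diabetes: 0.02, 0.05, 0.10, 0.15. It is kept low because known diabetes with an "uncontrolled risk factor or high A1c" is already a route to being targeted (section 5.b).
- pC, the share of these diagnosed in follow-up in Arm 2: 0.3. pT, the share in Arm 1: 0.4, 0.5, 0.6, 0.7.
- d, their change in risk minus that of other patients, with the label removed: −4, −2, 2, 4 points. The cap of 4 borrows from Statistical Power, where aggressive management moves risk by 4–5 points.

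Mean change among retained patients, relative to patients without diabetes, is m(p) = d·q(1 − p) / [q(1 − p) + 1 − q]. The bias is m(pT) − m(pC).

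- Extreme: q = 0.15, d = 4, pT = 0.7. 4 × 0.045/0.895 − 4 × 0.105/0.955 = 0.201 − 0.440 = −0.239. With d = −4 it is +0.239.
- Middle: q = 0.10, |d| = 2. Size 0.019, 0.039, 0.059 and 0.080 for pT = 0.4 to 0.7, with 3% excluded in Arm 2 and 4–7% in Arm 1.
- All 64 cells: median absolute bias 0.039. In 58 cells it is below 0.15, which is 10% of the 1.5-point effect. The other six have |d| = 4 with (q, pT) = (0.10, 0.7), (0.15, 0.6) or (0.15, 0.7).

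**Bias from keeping these patients with the score as observed.** If the label adds an assumed 2 or 4 points, the bias is q(pT − pC) × increment. It runs from 0.02 × 0.1 × 2 = 0.004 to 0.15 × 0.4 × 4 = 0.24, always against the tool. The middle case (q = 0.10, increment 2) is 0.02 to 0.08.

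**Second parametrisation.** Let p0 and p1 be the diagnosis rates among all targeted patients in Arms 2 and 1. Let D be the mean change of patients diagnosed only because of the tool, minus that of patients never diagnosed. The bias is −D(p1 − p0)/(1 − p0).

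| p0 | p1 | Size of D | Size of bias | Share of 1.5 points |
|---|---|---|---|---|
| 2% | 3% | 5 | 0.05 | 3% |
| 3% | 5% | 5 | 0.10 | 7% |
| 3% | 6% | 5 | 0.15 | 10% |
| 5% | 10% | 10 | 0.53 | 35% |

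The last row is deliberately extreme. Equal rates would not rule bias out: if the tool changes who is diagnosed in 1% of patients, then at |D| = 5 and a 3% rate the bias is 5 × 0.01/0.97 = 0.05.

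A simulation at 3% versus 6%, no true effect, gave −0.15 (D = 5) or +0.16 (D = −5) with the exclusion. Keeping the patients with a live label worth 5 points gave +0.16. Holding status at index gave +0.01, which is simulation noise.

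**Type I error.** This borrows the supplement's SD of change and assumes 60 clinics of 35 patients (1050 per arm) and an ICC of 0.02. SE = 11.51 × sqrt(2 × 1.68/1050) = 0.65, where 1.68 = 1 + 34 × 0.02. A nominal 0.05 becomes 0.050–0.052 in the middle case and 0.066 at the grid extreme (0.060–0.070 for ICC 0.05 to 0.01).

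**The case against.** The rule is stated in advance, applies to both arms and answers a real artefact. A new label raises the score even if care improved, so simply putting these patients back can bias against the tool by as much. The claim about confounding can be read narrowly, as meaning only that artefact. The middle-case bias barely moves the type I error. All of that stands, and it limits the point to a justification that does not hold and an unreported exclusion from the primary analysis.

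The size rests wholly on assumed inputs, which also stands. The plan's 4–5 points describe a treatment effect, not a difference in course between patients. With 5 in place of 4 the maximum becomes 0.239 × 5/4 = 0.30 (20% of 1.5 points), and 58 of 64 cells still lie below 0.15.

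The index visit falls after Arm 1 activation, so status recorded at that visit may already reflect the tool. Holding the same status in both the index and follow-up scores still stops a new label from moving the change score.

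**Conclusion.** The concern holds. The exclusion can bias the Aim 1 primary comparison in either direction, and its stated justification is wrong beyond the scoring artefact. The plan gives a reader no means of judging the effect.

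The bias is probably small: at most 0.24 points over the main grid, and 0.02 to 0.08 in the middle case. That judgement depends on assumed diagnosis rates and risk courses that the documents neither support nor contradict. The planned negative binomial or Poisson models do not estimate a mean difference, so the point values are indicative only. On these numbers neither exclusion nor the as-observed score is shown to be better. The change is worth making because a less biased method exists and the minimum check is cheap, not because a large bias has been demonstrated.

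**What to change.** Keep every targeted patient who meets the visit rule in the reversible-risk ITT analysis. Compute index and follow-up scores with diabetes status held at its index-visit value in both arms. Report new follow-up diagnoses by arm. Show the current exclusion and the as-observed score as sensitivity analyses; status fixed from pre-index records is an optional further one. State whether the exclusion applies to the treatment-on-the-treated analyses and to the 10-year ASCVD score.

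If the partner institute that owns the algorithm cannot rescore with status fixed, the minimum is to report the exclusions by arm, give the primary result with and without the exclusion, and delete the statement that it removes confounding.

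The minimum costs one SAP paragraph, one table row and one extra model run. The full version adds modest rescoring of newly diagnosed patients. The plan already has "CVD risk score / risk factor management status will be calculated at index visit and each encounter during follow-up", but no section shows that the tool can be run with status fixed. The downside is that a fixed-status score does not show a patient's actual risk after diagnosis, which is why the as-observed score stays as a sensitivity analysis.
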